#### Severe Events:

##### ***Stillbirth or myocardial infarction: Extremely rare***

Van Veen et al (2005) reported the only identified case of stillbirth in the English language literature after use of nifedipine. Importantly, this patient received multiple tocolytics (atosiban, indomethacin, nifedipine) which will not be the case in our study. Only 2 case reports were found of myocardial infarction associated with nifedipine tocolysis in the literature (Oei et al, 1999; Verhaert and Acker, 2004). In both cases healthy babies were ultimately delivered and there were no abnormalities on maternal follow-up testing. Importantly, in these cases nifedipine was used with another tocolytic (ritodrine), and in one case there were ruptured membranes. We will not be using nifedipine in conjunction with another tocolytic (in this case ritodrine), nor will we be using nifedipine in patients with ruptured membranes (at higher risk for infection). Of note, there have been 3 placebo-controlled trials of nifedipine for maintenance tocolysis over prolonged periods (Lyell et al, 2008; Parry et al, 2012; Roos et al, 2013). Importantly, none of these reported severe adverse events for nifedipine during the long periods that maintenance tocolysis was employed.

3. *Compare the risks of the research to standard of care. If placebo controls are used, justify their use over active or other kinds of controls.*

At Parkland Hospital, patients receive corticosteroids for fetal lung maturity, ampicillin as prophylaxis for Group B streptococcus, sedation and hydration. Tocolytic drugs are not used for preterm labor. However, use of tocolytic agents is within the standard of care for women with preterm labor. Given that it is uncertain whether nifedipine for acute tocolysis results in a benefit by delaying preterm birth and its associated risks, or only carries risks of side effects without benefits, it is ethical to compare nifedipine to placebo.

#### **11. Subject Safety and Data Monitoring:**

1. *Describe what measures have been taken and/or will be taken to prevent and minimize any risks or discomforts.*

Only singleton pregnancies in women with preterm labor and unruptured membranes will receive either placebo or nifedipine. Multiple tocolytics will not be used. Additionally, intravenous or sublingual (rapid-acting) forms of nifedipine will not be used. Only women with preterm labor at 28-0/7 weeks to 33-6/7 weeks will be included, as women with preterm labor between 24-0/7 weeks and 27-6/7 weeks receive magnesium sulfate for neuroprophylaxis and magnesium sulfate can synergize with nifedipine to block calcium movement through calcium channels. Women with hypotension, tachycardia or significant maternal cardiac disease or hypertension treated with antihypertensives will be excluded at the outset. Women with potential indications for delivery will be excluded. Hold dose parameters and stopping rule for further participation are detailed in Section 4(1) above.

2. *If applicable, discuss provisions for insuring necessary medical or professional intervention in the event of adverse events.*

All study participants will undergo regular vital sign monitoring while on Labor & Delivery and on the antepartum unit. Patients on Labor and Delivery will have continuous electronic fetal monitoring and tocometer evaluation, and patients on the antepartum unit will have daily fetal heart testing. If a maternal or fetal complication is identified, physicians will be immediately available to intervene on behalf of the mother and fetus.

3. Describe the plan for monitoring study data collected to protect subject safety and data integrity. Please review [Guidance on Data and Safety Monitoring Plans](#) for instructions on what information should be provided. If desired, the [DSMP Template](#) may be used and included in your application packet.

See DSMP

4. Note: investigator-initiated studies involving administration of an experimental (i.e. not FDA approved for the indication/population under study) drug, device or intervention **must** submit a Data Safety Monitoring Plan ([DSMP Template](#)) and may be required by the IRB to establish a Data Safety monitoring Board (DSMB).

See DSMP

### **Summary of Sections 66.0 and 67.0 of the Smart Form for the Data Safety Monitoring Plan and Committee**

*Who comprises the Data Safety Monitoring Committee (DSMC)?*

The DSMC is composed of [name], PhD, Professor and Statistician within the Department of Obstetrics and Gynecology, as well as two faculty physicians from the Department of Obstetrics and Gynecology not participating in the study ([name] and [name]).

*When will the DSMC meet:*

The DSMC will meet at least annually during the projected 4 year duration of the study. Additionally, after accrual of 75 patients (half of the planned 150 patients for recruitment), an interim analysis will be performed.

*What will be analyzed by the DSMC?*

The DSMC will monitor study accrual rate, study attrition including participant withdrawals/dropouts, patterns of AEs and/or unanticipated events, patterns of protocol deviations and/or violations and changes in risk/benefit. Efficacy (positive and negative) as well as possible futility of further study will be examined at the interim analysis. Significance levels for the interim analysis will be altered by the method of Lan-DeMets. Safety will be evaluated at each meeting of the Data Safety and Monitoring Board.

*How will safety be evaluated and what study-specific stopping rules will be used by the DSMC?*

Safety will be evaluated by analyzing situations in which administration of the study drug is stopped according to the "STOPPING RULE" below.

The study would be stopped if nifedipine is found to significantly delay preterm birth, or if a significantly greater number of stillbirths or emergency deliveries due to nonreassuring fetal heart tracing attributable to study drug during the 48 hour period during which the study drug will be administered for acute tocolysis of preterm labor.

*What safety mechanisms are built into the Nifedipine study protocol?*

Apart from the strict inclusion and exclusion criteria and the plan to continue maternal and fetal monitoring for at least 24 hours after beginning the study, the following safety parameters are part of the study protocol:

There will be a "HOLD DOSE" parameter in which a dose will be held if an enrolled patient either refuses medication or has a heart rate greater than 120. If a dose is held, the nurse will contact the 4th year resident who will ensure [name] is notified.

There will be a "STOPPING RULE" for further individual participation in the study for any of the following criteria: withdrawal of consent, diffuse rash or anaphylaxis reaction to medication (requires confirmation by house officer), hypotension requiring delivery or medication such as ephedrine, or development of any obstetrical outcomes that would normally preclude tocolysis

(development of ruptured membranes, development of chorioamnionitis, development of preeclampsia/gestational hypertension, development of bleeding suspicious for abruption, cervical dilatation of 6 cm or more or fetal death), or if a decision is made to either deliver the patient or to give regional anesthesia.

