## **13. Potential Benefits:**

1. *Describe the potential benefits of the research to the subjects, to others with similar problems, and to society. If there is no prospect of direct benefit to the subjects, state how the knowledge to be gained will benefit society enough to justify any risks to subjects.*

Potential direct benefits to the study participant are prolongation of pregnancy and avoidance of preterm birth. Potential benefits to society include a better understanding of whether nifedipine is an effective intervention for tocolysis of preterm labor.

**14. Biostatistics:** (omit this section for peer-reviewed research such as cooperative group, or NIH-sponsored studies, and for industry-sponsored research which has been submitted to FDA)

1. *Describe the statistical methods to be used to answer the study question(s). Pilot studies also require a method of analysis, but the justification of the target sample size is not required.*

T-tests (two-sided) will be used for continuous variables and Chi-squared tests for categorical variables. Power will be 80% and an alpha of 0.05 will be used.

2. *Explain how the target sample size was determined.*

Previous studies done on preterm patients at Parkland Hospital include Leveno et al (1986), Cox and Leveno (1990) and Chao et al (2011). In Chao et al (2011), there were 153 patients in 12 months. Over 4 years, we would anticipate four-times that ( $153 \times 4 = 612$ ). In Chao et al (2011, The Diagnosis and Natural History of False Preterm Labor, Obstet Gynecol), 27% of the patients diagnosed with contractions and with cervical dilation of less than 2 cm delivered prior to 37 weeks' gestation. However, this study by Chao et al was not a prospective study. Additionally, it focused on women with cervical dilatation less than 2 cm, whereas the current study includes women with cervical dilation of 2 to 4 cm dilated. Importantly, women with more cervical dilation are more likely to deliver early, and it is appropriate to revise the target enrollment.

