Fortunately, 2 prior Randomized, (placebo) Controlled Trials (RCT) of tocolysis (magnesium and ritodrine) from Parkland Hospital have been published. For the RCT by Leveno et al of ritodrine versus placebo (“Single-Centre Randomised Trial of Ritodrine Hydrochloride for Preterm Labour”, Lancet, 1986) in which women with singleton pregnancies and preterm labor with cervical dilation up to 4 cm, 39 of 52 (75%) patients randomized to the control group delivered between 27 and 35 completed weeks. Similarly, for the RCT of magnesium sulfate versus placebo by Cox and Leveno (“Randomized investigation of magnesium sulfate for prevention of preterm birth” Am J Obstet Gynecol 1990) in which women with singleton pregnancies and preterm labor with cervical dilation less than 5 cm, 55 of 80 (68.8%) of patients randomized to the control group delivered between 27 and 35 completed weeks’ gestation. These are important data derived from randomized, placebo-controlled, prospective trials done here at Parkland Hospital and we feel that our sample size should incorporate this prospectively obtained data. An average of the above preterm birth rates for these two RCTs at Parkland Hospital is 71.2% (39+55 / 52+80). In slight distinction to the above studies, for the current study, we are including women beginning at 28 weeks’ gestation, and we will be assessing preterm birth as delivery at less than 37 weeks. In theory, the preterm labor rate for delivery at less than 37 weeks (the primary outcome of the current trial) would be higher than this average preterm birth rate for women prior to 35 completed weeks’ gestation. However, using these prospectively obtained numbers from past studies of preterm labor at Parkland hospital, we would need approximately 150 women (75 women in each of the 2 arms) in order to detect a 1/3 reduction (from 71.2% to 47.5%) in the rate of preterm birth with 80% power and an alpha of 5%.

Analysis of internal obstetrics operations data indicates that for the month of March 2015, there were 10 women between 28-0/7 weeks and 33-6/7 weeks with preterm labor and a cervix of 2 to 4 cm dilation. Of these 10 women, 6 were ineligible for participation in the study (2 had diabetes in pregnancy, 1 women had a twin gestation, 1 women was only 15 years of age and 1 woman had bleeding concerning for abruption). Of the 4 eligible women in March of 2015, 2 elected to participate in the study, consistent with our ongoing consent rate of approximately 50%.

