Effective September 17, 2015, there has been a protocol change at the level of the Division of Maternal-Fetal Medicine at Parkland Hospital. This protocol change will be to give corticosteroids for fetal lung maturity to women with diabetes and to all women with hypertension who are at risk of preterm birth. This MFM Division level protocol change will affect this study of women at risk of preterm birth.

Given that 2 of the formerly ineligible women (due to diabetes) who presented in March 2015 would now be eligible due to the above protocol change, we estimate that up to 24 additional women (2 x 12 = 24) would be screened per year, and up to 12 additional women (50% of the 24 additional screened) would participate. Given that there were 29 women recruited over the initial 13 months (which equates to approximately 27 over 12 months), under the new practice in which corticosteroids will be given more broadly (and women with diabetes and mild hypertension not treated with medications are eligible for participation), we estimate that up to 78-90 women would now be screened, and of these, we estimate that 39-40 women would participate per year.

Therefore, over ~4-5 years, we would expect 300 patients screened and 150 patients consented. In order to detect a 33% reduction in the rate of preterm birth less than 37 weeks’ gestation, assuming 80% power and a 2-sided alpha of 5%, a sample size of 75 patients per arm (two arms, study drug and placebo), 150 patients total, will need to be recruited. So far in the current study, we have had about a 50% consent rate. Assuming a 50% recruiting rate (50% x 300 = 150), it is estimated that this study will take 4 to 5 years to complete.

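### Does naming Lan-DeMets for the interim look without a spending function leave the trial's error control open?

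*Combined protocol and SAP*

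**What the plan says.** Section 11 refers to the DSMP, which appears under the heading "Summary of Sections 66.0 and 67.0 of the Smart Form for the Data Safety Monitoring Plan and Committee". The data safety monitoring committee (DSMC) consists of a departmental PhD statistician and two physicians who take no part in the study. One interim analysis follows accrual of 75 of the 150 women. On its scope: "Efficacy (positive and negative) as well as possible futility of further study will be examined at the interim analysis". On the level: "Significance levels for the interim analysis will be altered by the method of Lan-DeMets". On the action: "The study would be stopped if nifedipine is found to significantly delay preterm birth".

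Section 14 (Biostatistics) specifies chi-squared tests for categorical outcomes and says "Power will be 80% and an alpha of 0.05 will be used". Its sample-size paragraph repeats this as "assuming 80% power and a 2-sided alpha of 5%, a sample size of 75 patients per arm". Section 14 does not mention the interim look. No section names a spending function or gives a nominal level for either analysis.

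**The concern.** Lan-DeMets is a family of boundaries. It gives a critical value only once a spending function is chosen, so the word that triggers stopping for efficacy has no number attached. Two common choices differ widely at half the information. The choice affects whether the trial stops at 75 women, whether a final p-value between 0.028 and 0.049 counts as significant, and how much power remains.

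Two features of the text sharpen the worry. It speaks of altering levels for the interim analysis only, while Section 14 keeps 0.05, so a reader could suppose that the final test is not adjusted. And a function left unrecorded could in principle be picked with the data in hand.

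**Working it through.** **Inputs.** Preterm birth 71.2% against 47.5%, 80% power, two-sided alpha 0.05, 75 per arm (Section 14). One look at 75/150, so the information fraction is t = 0.5 (Section 11, DSMP summary). The O'Brien-Fleming-type and Pocock-type functions are assumptions; the documents name neither.

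**1. The plan's own figure.** With mean rate 0.5935 and difference 0.237:

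n = [1.960·√(2·0.5935·0.4065) + 0.842·√(0.712·0.288 + 0.475·0.525)]² / 0.237² = (1.3615 + 0.5673)² / 0.05617 = 66.2 per arm.

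With continuity correction: (66.2/4)·[1 + √(1 + 4/(66.2·0.237))]² = 74.4, which rounds up to 75. The planned 75 is therefore the fixed-sample, continuity-corrected size, with no allowance for the interim look.

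**2. Thresholds at t = 0.5.**
- O'Brien-Fleming-type, two one-sided 0.025 functions: 4[1 − Φ(2.241/√0.5)] = 0.0031.
- O'Brien-Fleming-type, applied directly at two-sided 0.05: 2[1 − Φ(1.960/√0.5)] = 0.0056.
- Pocock-type: 0.05·ln(1 + 1.718·0.5) = 0.0310.

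The final critical value is then solved from the bivariate normal distribution with correlation √0.5, so that the total is 0.05.

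| Spending function | Interim p (z) | Final p (z) |
|---|---|---|
| O'Brien-Fleming-type, 0.025 per tail | 0.0031 (2.963) | 0.0490 (1.969) |
| O'Brien-Fleming-type, direct two-sided | 0.0056 (2.772) | 0.0478 (1.979) |
| Quadratic power | 0.0125 (2.498) | 0.0436 (2.018) |
| Linear | 0.0250 (2.241) | 0.0336 (2.125) |
| Pocock-type | 0.0310 (2.157) | 0.0277 (2.201) |

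Every row totals 5% by construction. The spread in the interim threshold is 0.0310/0.00305 = 10.2-fold, or 0.0310/0.00557 = 5.6-fold with the other O'Brien-Fleming-type form.

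**3. In events.** With 27/38 preterm births on placebo (71%) and a continuity-corrected chi-squared test, 12/37 on nifedipine gives p = 0.0018, 13/37 gives 0.0039 and 16/37 gives 0.0277. The look stops at 12 or fewer under the 0.0031 boundary and at 16 or fewer under the Pocock-type boundary.

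**4. Stopping and power at the planned effect.** Exact two-stage binomial, 38+37 women and then 75+75, using the first and last rows of the table:

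| Test | Function | Stops at 75 women | Power |
|---|---|---|---|
| Corrected | O'Brien-Fleming-type | 0.124 | 0.813 |
| Corrected | Pocock-type | 0.406 | 0.746 |
| Uncorrected | O'Brien-Fleming-type | 0.178 | 0.854 |
| Uncorrected | Pocock-type | 0.503 | 0.805 |

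Only one of the four combinations falls below 80%.

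**5. If the final test stayed at an unadjusted 0.05.** In the normal approximation without correction, total error is 5.1% (O'Brien-Fleming-type interim) or 6.9% (Pocock-type interim). With the corrected test, the exact totals are 3.3% and 4.2% at a common rate of 0.712, and 3.7% and 4.8% at 0.60. So the test that can lose power does not exceed 5% at these rates, and the test that can exceed 5% keeps its 80% power.

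**The case for a change.** The strongest case for a change is that pre-specification matters because it removes discretion. Lan-DeMets protects alpha only if the function is fixed before the outcomes are seen and used at both looks, and nothing in these documents records that. With 13 to 16 preterm births among 37 women on nifedipine, the trial would stop under one function and continue under another. Writing the choice down takes two or three sentences, and O'Brien-Fleming-type spending needs no extra women.

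The omission stands, and recording the choice would be good documentation. The rest is weaker. Spending a total alpha across all looks is what the named method does; a final test at an unadjusted 0.05 would be a departure from it, not a fair reading of it. Section 14 states a two-sided 5% for the 150-woman design, so only the word overall is missing. The look is triggered by accrual, so outcome information may be below one half. At an assumed t = 0.4 the interim levels become 0.0008 and 0.026, and spending functions are designed to accommodate such a shift. Finally, silence in a summary does not show that the underlying form is silent.

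**Conclusion.** No change to the plan follows. The method, the number of looks, their timing and the two-sided alpha are given, and a statistician sits on the committee that will compute the boundary. What is missing is one choice within a valid family, and any member fixed in advance and applied at both looks holds 5% to the usual normal approximation.

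The choice bears on when the trial would stop (interim threshold from about 0.003 to 0.031) and modestly on power (0.746 to 0.854 at 75 per arm). The stated 80% is lost only under two conditions together, Pocock-type spending and a continuity-corrected analysis, and the plan commits to neither. The conclusion assumes that the function is fixed before interim outcomes are seen and that the final level is taken from the same function. Nothing in the documents contradicts either assumption.

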## **12. Procedures to Maintain Confidentiality:**

1. *Describe how data/specimens will be collected and stored and the security methods in place. Note: the more sensitive the study data, the more sophisticated the methods should be to maintain confidentiality.*

Data on all obstetrical and neonatal outcomes are routinely entered into [name] obstetrical operations database (a secure, password-protected database at UT Southwestern).

2. *If data/specimens will be disclosed to outside persons or entities, list the entities and the method used to code or de-identify the data/specimens.*

No data or specimens are anticipated to be disclosed to any outside persons or entities.

3. *State if you intend to apply for a Certificate of Confidentiality from the NIH.*

N/A

## **13. Potential Benefits:**

1. *Describe the potential benefits of the research to the subjects, to others with similar problems, and to society. If there is no prospect of direct benefit to the subjects, state how the knowledge to be gained will benefit society enough to justify any risks to subjects.*

Potential direct benefits to the study participant are prolongation of pregnancy and avoidance of preterm birth. Potential benefits to society include a better understanding of whether nifedipine is an effective intervention for tocolysis of preterm labor.

**14. Biostatistics:** (omit this section for peer-reviewed research such as cooperative group, or NIH-sponsored studies, and for industry-sponsored research which has been submitted to FDA)

1. *Describe the statistical methods to be used to answer the study question(s). Pilot studies also require a method of analysis, but the justification of the target sample size is not required.*

T-tests (two-sided) will be used for continuous variables and Chi-squared tests for categorical variables. Power will be 80% and an alpha of 0.05 will be used.

2. *Explain how the target sample size was determined.*

Previous studies done on preterm patients at Parkland Hospital include Leveno et al (1986), Cox and Leveno (1990) and Chao et al (2011). In Chao et al (2011), there were 153 patients in 12 months. Over 4 years, we would anticipate four-times that ( $153 \times 4 = 612$ ). In Chao et al (2011, The Diagnosis and Natural History of False Preterm Labor, Obstet Gynecol), 27% of the patients diagnosed with contractions and with cervical dilation of less than 2 cm delivered prior to 37 weeks' gestation. However, this study by Chao et al was not a prospective study. Additionally, it focused on women with cervical dilatation less than 2 cm, whereas the current study includes women with cervical dilation of 2 to 4 cm dilated. Importantly, women with more cervical dilation are more likely to deliver early, and it is appropriate to revise the target enrollment.

Fortunately, 2 prior Randomized, (placebo) Controlled Trials (RCT) of tocolysis (magnesium and ritodrine) from Parkland Hospital have been published. For the RCT by Leveno et al of ritodrine versus placebo (“Single-Centre Randomised Trial of Ritodrine Hydrochloride for Preterm Labour”, Lancet, 1986) in which women with singleton pregnancies and preterm labor with cervical dilation up to 4 cm, 39 of 52 (75%) patients randomized to the control group delivered between 27 and 35 completed weeks. Similarly, for the RCT of magnesium sulfate versus placebo by Cox and Leveno (“Randomized investigation of magnesium sulfate for prevention of preterm birth” Am J Obstet Gynecol 1990) in which women with singleton pregnancies and preterm labor with cervical dilation less than 5 cm, 55 of 80 (68.8%) of patients randomized to the control group delivered between 27 and 35 completed weeks’ gestation. These are important data derived from randomized, placebo-controlled, prospective trials done here at Parkland Hospital and we feel that our sample size should incorporate this prospectively obtained data. An average of the above preterm birth rates for these two RCTs at Parkland Hospital is 71.2% (39+55 / 52+80). In slight distinction to the above studies, for the current study, we are including women beginning at 28 weeks’ gestation, and we will be assessing preterm birth as delivery at less than 37 weeks. In theory, the preterm labor rate for delivery at less than 37 weeks (the primary outcome of the current trial) would be higher than this average preterm birth rate for women prior to 35 completed weeks’ gestation. However, using these prospectively obtained numbers from past studies of preterm labor at Parkland hospital, we would need approximately 150 women (75 women in each of the 2 arms) in order to detect a 1/3 reduction (from 71.2% to 47.5%) in the rate of preterm birth with 80% power and an alpha of 5%.

Analysis of internal obstetrics operations data indicates that for the month of March 2015, there were 10 women between 28-0/7 weeks and 33-6/7 weeks with preterm labor and a cervix of 2 to 4 cm dilation. Of these 10 women, 6 were ineligible for participation in the study (2 had diabetes in pregnancy, 1 women had a twin gestation, 1 women was only 15 years of age and 1 woman had bleeding concerning for abruption). Of the 4 eligible women in March of 2015, 2 elected to participate in the study, consistent with our ongoing consent rate of approximately 50%.

Effective September 17, 2015, there has been a protocol change at the level of the Division of Maternal-Fetal Medicine at Parkland Hospital. This protocol change will be to give corticosteroids for fetal lung maturity to women with diabetes and to all women with hypertension who are at risk of preterm birth. This MFM Division level protocol change will affect this study of women at risk of preterm birth.

Given that 2 of the formerly ineligible women (due to diabetes) who presented in March 2015 would now be eligible due to the above protocol change, we estimate that up to 24 additional women (2 x 12 = 24) would be screened per year, and up to 12 additional women (50% of the 24 additional screened) would participate. Given that there were 29 women recruited over the initial 13 months (which equates to approximately 27 over 12 months), under the new practice in which corticosteroids will be given more broadly (and women with diabetes and mild hypertension not treated with medications are eligible for participation), we estimate that up to 78-90 women would now be screened, and of these, we estimate that 39-40 women would participate per year.

Therefore, over ~4-5 years, we would expect 300 patients screened and 150 patients consented. In order to detect a 33% reduction in the rate of preterm birth less than 37 weeks’ gestation, assuming 80% power and a 2-sided alpha of 5%, a sample size of 75 patients per arm (two arms, study drug and placebo), 150 patients total, will need to be recruited. So far in the current study, we have had about a 50% consent rate. Assuming a 50% recruiting rate (50% x 300 = 150), it is estimated that this study will take 4 to 5 years to complete.

